5. TREATMENT OF SUBJECTS

Not applicable (no intervention study)

6. INVESTIGATIONAL PRODUCT

6.1 Name and description of investigational product(s)

PSMA-HBED –CC consists of a PSMA binding sequence glutamate-urea-lysine coupled to the chelator HBED-CC which allows labelling with Ga-68. More information about the investigational product can be found in the IB (chapter 4: Physical, Chemical and Pharmaceutical Properties and Formulation, page 8) and the IMPD (chapter 2.1.S: drug substance, page 6)

6.2 Summary of findings from non-clinical studies

See the IB, chapter 5: nonclinical studies, page 11

6.3 Summary of findings from clinical studies

See the IB, chapter 6: clinical studies, page 13

6.4 Summary of known and potential risks and benefits

See the IB, chapter 6.2: safety and efficacy, page 15

6.5 Description and justification of route of administration and dosage

The final formulation of the product is ^{68}Ga - PSMA-HBED-CC in ethanol 7% in PBS (14 ml), 2MBq / kg / body weight ^{68}Ga , 10 μg PSMA-HBED-CC, which is administered intravenously in a single injection. This is in line with previous studies on the investigational product for prostate cancers patients.

6.6 Dosages, dosage modifications and method of administration

Dosage and method of administration are mentioned above. Dosage modifications are not applicable as participants get only one dose.

6.7 Preparation and labelling of Investigational Medicinal Product

Information about the preparation of the investigational product can be found in the IMPD (chapter 2.1.S.2: Manufacture, page 8). Information about labelling can also be found in the IMPD (chapter 2.1.P.7: ContainerClosureSystem, page 28).

6.8 Drug accountability

The investigational product will be produced on site (Department of Radiology and Nuclear Medicine, Radboudumc). The investigational product is dispensed in a closed 20ml sterile glass type 1 vial with a sterile bromobutyl stopper (sealed with an aluminium cap), and labeled as depicted on page 28 of the IMPD. These labels of the bulk vial are only to be used for internal use in the cleanroom in which the product is dispensed and in which aseptic compounding is performed ("Hotlab"). Labeling of the patient dose in the syringe complies to annex 13 and is also shown on the same page. After aseptic compounding of the patient dose, the remaining solution is stored as retention sample.

7. NON-INVESTIGATIONAL PRODUCT

Not applicable

8. METHODS

8.1 Study parameters/endpoints

8.1.1 Main study parameter/endpoint

The SUV of ⁶⁸Ga-PSMA estimated with ⁶⁸GA-PSMA-PET scanning. If the SUV of tumor tissue is higher than the SUV of healthy salivary gland tissue and/or comparable to the SUV in prostate cancer, the level of PSMA expression is deemed high enough to pursue a therapeutic study with ¹⁷⁷Lu-PSMA.

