In the current study, we will evaluate the uptake of ^{68}Ga -PSMA by performing ^{68}Ga -PSMA-PET/CT scans in locally advanced, recurrent and metastatic ACC/SDC patients. Tumor uptake will be measured quantitatively. The tumor-to-background ratio and tumor-to-‘healthy salivary gland tissue’ ratio will be calculated. Tumor uptake will also be correlated to the degree of immunohistochemical PSMA expression of the primary tumor on archival tissue.

This study is of relevance for patients with locally advanced, recurrent or metastatic ACC/SDC because treatment options are very limited and ^{177}Lu -PSMA could be a promising new treatment option. In prostate cancer, ^{177}Lu -PSMA therapy has proven its value as stated above. In ACC/SDC this therapy may also be effective because PSMA expression in ACC/SDC is observed immunohistochemically and in a case report on ^{68}Ga -PSMA-PET/CT imaging in ACC.¹² In order to establish whether ACC/SDC patients are eligible for ^{177}Lu -PSMA therapy, the level of PSMA expression has to be established with ^{68}Ga -PSMA-PET/CT scans. This is the goal of this study. If this study indeed shows sufficient PSMA expression, a therapeutic study with ^{177}Lu -PSMA will be started in next future.

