2. OBJECTIVES

Primary Objective: To evaluate the uptake of ^{68}Ga -PSMA in locally advanced, recurrent and metastatic ACC/SDC by performing ^{68}Ga -PSMA-PET/CT scans.

Secondary Objective(s):

- To calculate the SUV tumor-to-background ratio and tumor-to-'healthy salivary gland tissue' ratio.
- Correlate the tumor uptake (SUV) to the degree of immunohistochemical PSMA expression of the primary tumor on archival tissue.
- To establish whether new metastatic lesions are found by ^{68}Ga -PSMA-PET/CT imaging

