8.1.2 Secondary study parameters/endpoints

- the SUV tumor-to-background ratio
- the SUV tumor-to-‘healthy salivary gland tissue’ ratio.
- The correlation between the SUV and the degree of immunohistochemical PSMA expression of the primary tumor on archival tissue.
- The establishment of new metastatic lesions.

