10. STATISTICAL ANALYSIS

10.1 Primary study parameter(s)

SUV will be calculated according to the following formula:

(measured activity concentration [MBq/mL] * body weight [g]) / injected activity [MBq]

The PET/CT images will be reconstructed in three dimensions. The PET and CT images will be fused and the SUVs will be aligned with CT to assess ⁶⁸Ga-PSMA uptake in tumor lesions, healthy salivary gland tissue, and the background.

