10.2 Secondary study parameter(s)

Tumor-to-background ratios and tumor-to-'healthy salivary gland tissue' ratios will be calculated using the SUV. It will be presented as mean and standard deviations.

Immunohistochemical PSMA expression on a tissue sample of the primary tumor will be quantified using a four point scale for tumor PSMA expression (0 = no expression, 1 = weak expression, 2 = moderate expression, and 3 = strong expression) and the number of PSMA-positive blood vessels per mm² will be counted.

The correlation between the immunohistochemical PSMA expression and tumor SUV will be evaluated using linear regression analysis. A p-value of <0.05 will be considered significant. Analyses will be performed using SPSS version 22.0.

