In ACC and SDC, the investigational product has not been evaluated before and is therefore not yet predictable. In this study we will correlate the SUV of the primary tumor with the level of immunohistochemical PSMA staining on archival tissue to establish whether the efficacy of PSMA-PET imaging can be predicted with immunohistochemistry.

j. Can effects be managed?

No side effects which require to be managed have been reported in the literature. However, if a participant develops unexpected side-effects, the study center (Radboudumc) can deliver adequate medical support of emergencies.

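### Does the lack of a rule for turning several lesion SUVs into one tumour value undermine the decision on a therapeutic study?

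*Combined protocol and SAP*

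**What the plan says.** Section 8.1.1 names the SUV as the main endpoint and attaches a decision to it: a therapeutic study is justified "If the SUV of tumor tissue is higher than the SUV of healthy salivary gland tissue and/or comparable to the SUV in prostate cancer". Section 1 says the same in general terms: "If this study indeed shows sufficient PSMA expression, a therapeutic study with" the lutetium-labelled ligand is to follow.

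Section 10.1 gives the SUV formula and says the fused images will be used to assess "uptake in tumor lesions, healthy salivary gland tissue, and the background". It does not say whether the value within a lesion is the maximum, mean or peak, which lesions are measured, or how they are summarised within a patient.

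Section 10.2 says of the tumour-to-background and tumour-to-gland ratios: "It will be presented as mean and standard deviations". It does not say whether the mean runs over lesions or patients. It adds: "The correlation between the immunohistochemical PSMA expression and tumor SUV will be evaluated using linear regression analysis".

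Section 4.2 admits locally advanced, recurrent and metastatic disease, and section 8.3 scans from groin to skull top, so several lesions per patient are to be expected. Section 4.4 sets 15 ACC and 10 SDC patients without a calculation, because no baseline uptake data exist.

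**The concern.** The comparison in 8.1.1 needs one number per patient, or one for the group, while the scan yields several. The maximum of a set is never below its mean, so the open choice can move the result in one direction only, towards tumour above gland. In a patient whose lesions lie on both sides of the gland value, the same scan can be read either way. If the summary is chosen after the scans are read, the reader's choice could decide the comparison.

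Two further points seem to add to this. The ratios in 10.2 have no stated unit of analysis. Section 13.1(i) says "In this study we will correlate the SUV of the primary tumor with the level of immunohistochemical PSMA staining on archival tissue", which taken literally cannot be done where the primary has been resected.

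**Working it through.** **Plan's own figure.** There is none to reproduce: section 4.4 declares a calculation not applicable. Everything below is illustration on assumed inputs.

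**1. Can the readings differ?** Take five lesions at 0.4, 0.6, 0.7, 0.9 and 1.4 times gland SUV. The hottest is 1.4 (above gland). The mean is 4.0/5 = 0.8 and the median 0.7 (both below). So they can.

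**2. By how much?** Assume lognormal lesion SUVs with a within-patient CV of 30 to 50% and 3 or 5 lesions. The log SD is sqrt(ln(1 + CV²)): 0.294 at 30% and 0.472 at 50%. The expected maximum of k standard normals is 0.846 (k = 3) or 1.163 (k = 5). Hottest over geometric mean is exp(expected maximum × log SD):

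| CV | k = 3 | k = 5 |
|---|---|---|
| 30% | 1.28 | 1.41 |
| 50% | 1.49 | 1.73 |

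Against the arithmetic mean, which is the more natural reading of the word in 10.2, simulation gives about 1.25 to 1.6.

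**3. How many patients would be classified differently?** Model the standardised log tumour-to-gland ratio as mu + patient effect + lesion effect, with total variance 1. Mu is the probit of the share of lesions above gland, the correlation between a patient's lesions is 0.3 to 0.7, and k is 3 or 5. With 400,000 simulated patients per setting, the proportion above gland is:

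| Share of lesions above gland | Hottest lesion | Geometric mean |
|---|---|---|
| 10% | 19 to 34% | 3 to 8% |
| 30% | 47 to 71% | 21 to 28% |
| 40% | 59 to 82% | 35 to 39% |
| 70% | 85 to 98% | 72 to 79% |

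Of 25 patients, the 30% row is about 12 to 18 against 5 to 7. With the arithmetic mean, 21 to 28% becomes about 26 to 32%. These are patient counts only: the protocol sets no majority or other count that would turn them into a decision.

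**4. How far do the assumptions drive this?** A second model has independent lesions, a fixed gland value, a mean tumour-to-gland ratio of 0.5 to 0.9 and a CV of 0.3 to 0.8. The share of patients in whom hottest and arithmetic-mean readings disagree is 0% with one lesion, 1 to 25% with two, 3 to 65% with five and 6 to 85% with ten. That range is too wide to say whether this trial would be affected.

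**5. The immunohistochemistry regression.** Assume 25 patients, a staining-score distribution of 15/20/30/35%, and 1, 3, 5 or 8 lesions equally likely. With one row per patient and a true correlation of 0.6, power at lesion correlations of 0.3, 0.5 and 0.7 is about 60, 77 and 86% using the average, and 40, 62 and 78% using the hottest lesion. With no true association, either summary keeps type I error near 5%. If each lesion were entered as an independent row, type I error would be about 21 to 36%. The tissue score is one value per patient, so one row per patient is the natural layout.

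**6. The primary-tumour wording.** Section 2 reads "Correlate the tumor uptake (SUV) to the degree of immunohistochemical PSMA expression of the primary tumor on archival tissue" and section 8.1.2 reads "The correlation between the SUV and the degree of immunohistochemical PSMA expression of the primary tumor on archival tissue". Both attach the primary tumour to the stained tissue, as does 10.2. Only the risk section attaches it to the SUV. Three statements in the operative sections outweigh one in the risk analysis, so this is a slip of wording.

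**The case for a change.** The best case for a change is that the protocol itself attaches a decision to this number, so calling the study exploratory does not excuse the gap. The freedom runs only towards a positive finding. Section 4.4 says that failure in these patients means the technique will be judged not valuable. A few sentences fixed before the scans are read would remove the freedom without extra scans, tissue or patients. Nothing elsewhere fills the gap: the mean and SD in 10.2 cover the secondary ratios only, and 13.1(i) concerns only the tissue correlation.

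Much of this stands. The omission is genuine, and neither redaction nor text extraction explains it. Settling the summary before the scans are read is good practice, and a report that left the SUV measure, lesions and unit unstated would be open to criticism.

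Three things weaken it as a ground for changing the plan. First, a lesion rule would not make the decision mechanical: comparability with prostate cancer joins the gland comparison by and/or and has no figure, and no formal test is attached to either. Second, there is no uniquely right rule. A geometric mean of the largest lesions on CT would be defensible, but it would omit lesions seen only on PET, although new lesions are a secondary endpoint, and would leave a patient with no qualifying lesion without a value. The hottest lesion and the arithmetic mean have their own merits. Third, the size of the effect rests wholly on assumed inputs.

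**Conclusion.** No change to the plan is called for. Section 10.1 leaves a definition unwritten; it does not prescribe a method shown to be wrong, and the documents show only that a reading could mislead, not that following the plan would. The possible difference is large on some assumptions (47 to 71% of patients against 21 to 28% when 30% of lesions exceed gland) and nil on others (one lesion, or all lesions on one side of gland). Lesion number, spread, within-patient correlation and tumour-to-gland ratio are all assumed.

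This is a gap that analysts fill sensibly in a 25-patient first look at uptake. They would choose an SUV measure and a per-patient summary, compare it with the same patient's gland, keep one row per patient in the regression, and state these choices, showing both hottest and average values where they disagree. A reader can then judge the gland comparison. The wording in 13.1(i) is a clerical slip that sections 2, 8.1.2 and 10.2 resolve.

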4.4 Sample size calculation

The main purpose of this study is to establish the feasibility and value of ⁶⁸Ga-PSMA-PET/CT scans as a non-invasive method to assess PSMA expression in ACC/SDC patients. An exact sample size calculation is not applicable, because baseline information concerning the uptake of ⁶⁸Ga-PSMA in ACC/SDC patients is not available. Therefore we will establish ⁶⁸Ga-PSMA-PET/CT scanning in 15 ACC and 10 SDC patients. If the technique does not prove its value in these patients, we will conclude that it is not a valuable imaging technique for ACC/SDC patients.

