10.4 Interim analysis

Not applicable

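### The gland limb of the go rule in 8.1.1 turns on a bare comparison of tumour and gland SUV, with no measure of uncertainty attached

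*Combined protocol and SAP*

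**What the plan says.** All references are to the combined protocol and SAP.

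- **Section 8.1.1** makes the primary endpoint a study-level decision. The first limb reads "If the SUV of tumor tissue is higher than the SUV of healthy salivary gland tissue". It continues "and/or comparable to the SUV in prostate cancer, the level of PSMA expression is deemed high enough to pursue a therapeutic study". Because the limbs are joined by and/or, the first is sufficient alone.
- **Section 10.1**, the primary analysis, gives the SUV formula and the image handling: "the SUVs will be aligned with CT to assess ⁶⁸Ga-PSMA uptake in tumor lesions, healthy salivary gland tissue, and the background". It names no summary statistic, interval or test for tumour against gland.
- **Section 10.2** calculates the tumour-to-gland ratio as a secondary parameter: "It will be presented as mean and standard deviations". It does not link the ratio to the rule in 8.1.1. The sentence "A p-value of <0.05 will be considered significant" follows the regression of SUV on immunohistochemistry, not this comparison.
- **Section 4.4** sets the numbers, "Therefore we will establish ⁶⁸Ga-PSMA-PET/CT scanning in 15 ACC and 10 SDC patients", and gives no error rate: "An exact sample size calculation is not applicable, because baseline information concerning the uptake of ⁶⁸Ga-PSMA in ACC/SDC patients is not available". It adds that if the technique does not prove its value in these patients, it will be judged not valuable.
- **Section 8.5** replaces withdrawals, so the numbers stay at 15 and 10. **Section 10.4** plans no interim look, so the rule is applied once.

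**The concern.** The rule treats an observed ratio just above 1 in 10 patients as the same evidence as a ratio of 3. A reader of the final report would see a verdict, a mean and an SD, but nothing showing how firmly the data place tumour uptake above gland uptake.

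A ratio near 1 cannot be ruled out in advance. Section 13.1 notes that healthy salivary glands take up the tracer in prostate cancer patients, and section 4.4 says that no baseline uptake data exist for ACC or SDC. A bare comparison separates the possibilities least well in that region. The verdict has consequences: section 1 says that a therapeutic study will follow if expression is sufficient, and section 4.4 draws a negative conclusion from the same patients.

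**Working it through.** The plan states no error rate or power for this rule, so there is no figure to reproduce.

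**Inputs.** n = 15 (ACC) and 10 (SDC), from section 4.4. The between-patient SD of the log tumour-to-gland ratio is not in the documents; 0.4 to 0.8 is assumed. The summary is also assumed: the mean within-patient log ratio, one comparison per histology.

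**1. The limb as written.** P(go) = Φ( ln(true ratio) / (SD/√n) ). The standard error SD/√n is 0.103 to 0.207 for n = 15 and 0.126 to 0.253 for n = 10.

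| True ratio | ln(ratio) | n = 15 | n = 10 |
|---|---|---|---|
| 1.0 | 0 | 50% | 50% |
| 0.9 | −0.105 | 15-30% | 20-34% |
| 0.8 | −0.223 | 2-14% | 4-19% |

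Example: n = 10, SD 0.8, ratio 0.9 gives Φ(−0.105/0.253) = Φ(−0.416) = 34%. At a ratio of 1 the argument is zero, so the result is 50% for any n and any SD.

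**2. Other readings of the same sentence.**
- *Mean of raw ratios*, the only summary that 10.2 names. With log-normal ratios of median 1 and the same SDs, simulation gives P(mean ratio > 1) of 76-89% (n = 15) and 71-84% (n = 10). The expected raw ratio here is exp(SD²/2), that is 1.08 to 1.38, so part of this is a scale effect, and it rises with n.
- *Majority of patients with tumour above gland*, each with probability 0.5: 50% (n = 15) and 38% (n = 10), or 62% (n = 10) if a 5/5 split counts as a go.
- *A go in either histology*, both with a true ratio of 1 under the reading in step 1: 1 − 0.5² = 75%.

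**3. What an interval would do.** Call the limb supported when the one-sided 95% lower t limit of the mean log ratio exceeds 0, that is, when the ratio's lower limit exceeds 1. At a true ratio of 1 this happens 5% of the time. The smallest observed geometric mean ratio that qualifies is exp(t·SD/√n). With t = 1.761 on 14 df it is 1.20 to 1.44; with t = 1.833 on 9 df it is 1.26 to 1.59. The probability of supported comes from the non-central t with non-centrality ln(ratio)·√n/SD:

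| True ratio | n = 15, SD 0.8 to 0.4 | n = 10, SD 0.8 to 0.4 |
|---|---|---|
| 1.5 | 59% to 98% | 43.5% to 90% |
| 2.0 | 94% to nearly 100% | 81% to nearly 100% |

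**4. What it would not do.** The 5% is for one limb in one histology. If a result in either histology counts, two independent 5% tests give 1 − 0.95² = 9.75%, about 10%. The limb on comparability with prostate cancer can add further go decisions and has no stated error rate.

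**The case against.** **This is a 25-patient feasibility study, and a go leads only to another study, in a disease that section 1 says has very limited treatment options.** A confidence-limit gate is then one defensible choice among several, and the cost of stopping wrongly may outweigh that of proceeding wrongly. This stands against making the gate mandatory. It does not stand against printing an interval, which needs no prior data.

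**A reader might infer that the plan has a 50% false-go rate.** The documents do not support that as a fact. The 50% needs a single comparison on a symmetric scale, and 8.1.1 fixes neither the summary nor the level of pooling. The word false is also a judgement: nowhere do the documents say that equal uptake makes a therapeutic study wrong. Healthy gland is not a zero-uptake control, and uptake comparable to prostate cancer is accepted as sufficient without exceeding gland.

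**A reader might also blame the small sample.** At a true ratio of 1, more patients would not lower the 50%; it belongs to any point-estimate rule judged at its own threshold. Sample size matters only away from 1, and there the difference between 10 and 15 patients is modest.

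**An undecided category has no place in section 4.4** and could be read there as a failure to prove value. This stands, and the change must cover 4.4.

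**Conclusion.** The concern holds in a limited form. Under 8.1.1 an observed excess of any size on the gland limb is enough for a go, and the plan gives no measure of uncertainty for that comparison. How often equal or slightly lower uptake would pass depends on a reading that the plan leaves open. Step 1 quantifies one reading under assumed SDs, and step 2 shows that others run from 38% to 89% at equal uptake, for one histology. None of the readings calculated comes near a conventional 5%.

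The documents do not support the stronger conclusions that the rule is invalid or that the lower limit must exceed 1 before a therapeutic study is pursued. The defect is that the verdict would be reported without its precision and with no outcome between yes and no.

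**What to change.** - **8.1.1 and 10.2:** evaluate the gland limb on the within-patient log tumour-to-gland ratio, separately for ACC and SDC. This needs one tumour and one gland value per patient, so state how lesions are reduced to one value.
- **Same sections:** print the back-transformed ratio and its confidence interval beside the verdict. Report the limb as supported (interval above 1), not supported (below 1) or undecided (spans 1). Fix the confidence level before data; a two-sided 90% interval corresponds to the one-sided 95% limit used above.
- **4.4:** say that undecided is not a negative result.
- **Sponsor's decision, to be recorded in advance:** whether supported is required before a therapeutic study is pursued, and whether one histology is enough.

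**Cost.** Wording in three sections; no extra patients, scans or visits. The downside is more undecided results. At a true ratio of 1.5, the chance that SDC is not reported as supported is 10% to 56.5% over the assumed SDs (100% minus the step 3 figures). A one-sided 90% limit eases this: at SD 0.6 the SDC figure falls from 37% to about 22%, with 10% instead of 5% supported at a true ratio of 1. The change leaves the prostate-cancer limb and the either-histology question uncontrolled.
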